Background and Rationale:	Reconstruction of the anterior cruciate ligament (ACL) using autograft tissue is currently recommended as the standard of care following an ACL tear or rupture, with the bone-tendon-bone (BTB) graft and hamstring tendon graft the most common. Although a BTB autograft is widely recognized to offer high mechanical performance and rapid graft healing, these advantages come at the cost of a longer surgery time and higher risk of severe patient discomfort at the graft harvest site. Use of a hamstring tendon autograft is less painful, but is generally slower to heal with higher risk of mechanical graft failure due to poor bone ingrowth. The aim of the current study is to augment graft-to-bone incorporation by use of an osteoconductive scaffold enlaced into the hamstring tendon autograft. This bovine derived composite bone substitute is inserted into the articular aperture of the femoral bone tunnel and should provide an osteoconductive / osteoinductive environment at a biomimetic attachment site leading to improved secondary graft-fixation and a reduced incidence of tunnel widening.
Objective(s):	
Primary objective of the study is to evaluate efficacy of the surgical technique for ACL reconstruction using an osteoconductive scaffold, enlaced into the hamstring tendon autograft, compared to the traditional technique.
 
Secondary objectives aim to assess the clinical outcome of the interventional treatment including patient subjective knee function and objective measures of knee stability.

Outcome(s):	
The primary efficacy outcome of this study will be the CT based relative change of the femoral bone tunnel volume.
 
Secondary outcome measures for patient subjective knee function include International Knee Documentation Committee Subjective Knee Evaluation Form, Lysholm Knee Scoring Scale and Tegner Activity Scale. Knee stability will be assessed using the KT-1000 Arthrometer Test, the Lachman Test and the Pivot Shift Test.
 
Safety will be evaluated by the occurrence, frequency and severity of intra- and postoperative complications.

Study design:	Randomized patient-blinded two-group parallel comparison trial using an active comparator.

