Das vordere Kreuzband verläuft im Kniegelenk von der Oberschenkelrolle zum Schienbeindach und stabilisiert zusammen mit dem hinteren Kreuzband das Kniegelenk. Durch diese Führung werden andere Strukturen des Kniegelenks wie Menisken und Knorpel gegen eine Zerstörung geschützt. Rupturen des Kreuzbandes treten häufig in Sportarten die schnelle Richtungswechsel beinhalten (z.B. Fussball, Basketball) und im Bereich Ski Alpin auf. Zur Rekonstruktion des vorderen Kreuzbandes wird meist körpereigenes Material als Transplantat verwendet. Hierzu wird das mittlere Drittel des Kniestiegenbands (Patellarsehne) mit je einem kleinen Knochenblock aus der Kniestiege und dem Unterschenkel entnommen. Alternativ können auch Beugesehnen an der Innenseite des Kniegelenks (Semitendinosus- oder Gracilisseehne) als Transplantat verwendet werden. Das Transplantat wird mittels Kniegelenkspiegelung (arthroskopisch) in Bohrkanälen im Oberschenkel respektive im Unterschenkel mit Hilfe von Schrauben oder Stiften fixiert. Die Verwendung des Kniestiegenbands bietet hierbei den Vorteil eines beschleunigten Einwachsens des Transplantats in den Bohrkanal. Jedoch können an der Entnahmestelle Komplikationen wie Schmerzen und Kniestiegenfrakturen auftreten. Da bei der Verwendung einer Beugesehne kein Knochenblock entnommen wird, ist deren Entnahme unproblematischer, der Heilungsverlauf im Bohrkanal aber oft langwieriger. Das zu testende Medizinprodukt besteht aus einem knochenwachstumsinduzierenden Knochenersatz. Dieser soll das Einwachsen des Beugesehnentransplantats in den Bohrkanal beschleunigen. Der Knochenersatz wird in das Sehnentransplantat eingefädelt und kommt nach dessen Einziehen am gelenksnahen Ende des Bohrkanals im Oberschenkel zu liegen.

Zweck dieser Studie ist es, bei insgesamt 56 Patienten den Heilungsverlauf nach Kreuzbandrekonstruktion mit der zu untersuchenden Technik, mit der herkömmlichen Methode zu vergleichen. Primär untersucht wird das Auftreten von etwaigen Komplikationen sowie die Verknöcherung des Bohrkanals, ermittelt durch radiologische Untersuchungen. Hierzu werden der Heilungsverlauf, sowie die Patientenzufriedenheit und die Kniestabilität über einen Zeitraum von 5 Jahren verfolgt.

ABBREVIATIONS

ACL	Anterior cruciate ligament
AE	Adverse Event
BPTB	Bone patellar tendon bone
BTW	Bone tunnel widening
CA	Competent authorities (Swissmedic)
CEC	Competent Ethics Committee
ClinO	Clinical Trials Ordinance
CRF	Case Report Form
CT	Computed Tomography

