4.4 Safety Objectives

Safety will be evaluated by the occurrence, frequency and severity of intra- and postoperative complications.

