5.4 Safety Outcomes

Any occurrence of intra-operative complications will be recorded on the eCRF. Post-operative (serious) adverse events will be recorded at each follow-up visit.

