9.2.4.3 Assessment during Surgery

The following information will be gathered at surgery:

- Date of surgery
- Comorbidities (if any) determined arthroscopically
- Additional surgical procedures (if any) not leading to patient exclusion (e.g. partial meniscectomy, meniscus repair)
- Side of autograft harvest (ipsilateral/contralateral)
- Tendon used (semitendinosus tendon with/without Gracilis tendon)
- Diameter of the femoral bone tunnel
- Diameter of the tibial bone tunnel
- Duration of the surgical procedure

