9.2.5 Assessment of Safety Outcomes

9.2.5.1 Adverse Events

Intra-operative complications (if any) will be recorded on the eCRF. Self-reported AEs will be assessed by interviewing the patient. The following question will be used:

“Hatten Sie im Zusammenhang mit Ihrer Knieoperation irgendwelche nennenswerten medizinischen Probleme?”

Also any out of window visit or unexpected finding will be recorded. The following adverse event information will be recorded:

- Adverse event term
- Date of onset
- Date of resolution/Duration
- Severity (Subjective assessment by PI)
- Seriousness
- Relationship with surgical intervention
- Relationship with device under study
- Actions taken in response
- Outcome of the adverse event

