11.4.6 Safety Analysis

Safety will be evaluated by tabulations of AE's and SAE's and will be presented with descriptive statistics at baseline and follow-up visits for each treatment group. Inferential analyses of (serious) adverse events are not done.

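### Section 11.4.6 specifies adverse events only descriptively by visit and arm, with no per-patient proportion, denominator or interval, and sections 8.8 and 7.4 could take affected patients out of the tables

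*Combined protocol and SAP*

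**What the plan says.** All references are to the combined protocol and SAP.

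- **Objective (section 4.4):** "Safety will be evaluated by the occurrence, frequency and severity of intra- and postoperative complications".
- **Collection (sections 5.4 and 9.2.5.1):** intra-operative complications go on the eCRF, and "Post-operative (serious) adverse events will be recorded at each follow-up visit". The study schedule has five follow-up visits (Visits 3 to 7). Each event record holds a term, an onset date and "Date of resolution/Duration", among other items.
- **Analysis (section 11.4.6):** adverse events and serious adverse events are tabulated and "will be presented with descriptive statistics at baseline and follow-up visits for each treatment group". The section closes with "Inferential analyses of (serious) adverse events are not done".
- **Intervals (section 11.4):** the only confidence interval named is the one that accompanies the t-test.
- **Removal of patients:** under section 8.8, a patient with a complication during reconstruction with the investigational product is left out of further analysis and the reason is recorded. Under section 7.4, a graft rerupture leads to exclusion. Section 10.1.1 lists graft rupture among six findings that may need action.
- **Withdrawn patients (sections 8.7 and 9.2.6):** the site tries to contact them for safety information, by telephone interview.

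**The concern.** The objective needs, for each arm, the number of patients who had a complication out of the number at risk. The only presentation that section 11.4.6 specifies is by visit. It does not say whether patients or events are counted, what the denominator is, or how an event that spans several visits is treated. A reader of by-visit tables cannot in general recover how many different patients were affected.

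The denominator is also exposed. The rule in section 8.8 can act only in the intervention arm, because it is triggered by a complication while the device is being used. Its wording does not limit the exclusion to efficacy. Rerupture, which section 7.4 turns into an exclusion, is itself one of the complications a safety analysis should count. If these patients leave the tables, the events that bear most directly on the device leave with them.

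Section 3.3.1 reports that clinical investigations of the product so far were confined to oral, maxillofacial and cranial surgery. This trial's estimate of complication risk in ACL reconstruction therefore matters.

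**Working it through.** **1. Number per arm.** Inputs from section 11.2: difference 20%, SD 25.175%, two-sided α 0.05, power 0.80, drop-out 10%.

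n = 2 × (1.960 + 0.842)² × (25.175/20)² = 2 × 7.849 × 1.584 = 24.9, so 25 per group. Then 25/0.9 = 27.8, so 28 per arm and 56 in total. This reproduces the plan. (The noncentral t gives 26 per group, with power 78.6% at 25; this does not affect the present point.) The plan states no safety figure to reproduce.

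**2. What zero events would show.** The exact upper limit for 0/n is 1 − 0.025^(1/n) two-sided and 1 − 0.05^(1/n) one-sided.

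| n | two-sided 95% | one-sided 95% |
|---|---|---|
| 28 (randomised) | 12.3% | 10.1% |
| 25 (after drop-out) | 13.7% | 11.3% |

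Section 11.4 makes all tests two-sided, so the two-sided limit fits the plan's convention. Chance of seeing no event in 28 patients: 0.95^28 = 0.24 if the true risk is 5%, and 0.98^28 = 0.57 if it is 2%.

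**3. Difference between arms (Newcombe intervals).**
- 0/28 v 0/28: the Wilson upper limit is 3.84/(28 + 3.84) = 12.1%, so the interval is −12.1 to +12.1 percentage points.
- 3/28 v 0/28: difference 10.7 points, interval −3.2 to +27.2.

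**4. Why the counting unit matters.** Take one patient with one complication lasting from Visit 3 to Visit 7. Per patient this is 1/28 = 3.6%. If it were entered at each visit and the entries summed, it would be 5/28 = 17.9%. The plan does not prescribe such summing, but it gives no rule that settles the matter.

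**5. Why the denominator matters.** Suppose one intervention patient has a complication while the device is being used, and no one else has an event.
- Kept in: 1/28 = 3.6%, exact 95% interval 0.1% to 18.3%.
- Left out under section 8.8: 0/27, interval 0 to 1 − 0.025^(1/27) = 12.8%.

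The same data give one device complication or none, depending on how section 8.8 is read.

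**The case against.** Descriptive safety reporting without tests is an explicit choice and usual at this size. That stands: the gap is the missing estimate and its precision, and no test is needed. It is also true that an interval displays imprecision without reducing it; 12.3% follows from 28 patients per arm, a number set for tunnel volume. Intervals for many findings will be wide, and some readers may treat them as tests.

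Several stronger readings are tempting, but the documents do not support them.

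- A reader might infer that persisting events will be counted repeatedly. The plan leaves this open and does not prescribe it. The onset and resolution dates in section 9.2.5.1 allow each episode to be identified once.
- A reader might infer that zero events would be declared safe. No section sets a safety claim, margin or success rule.
- A reader might infer that patients under sections 8.8 and 7.4 are certainly lost to the safety tables. Sections 8.7 and 9.2.6 seek safety information from those who withdraw, and section 11.5 says all of a subject's data are used. The sections pull in different directions; none settles it.
- A reader might infer that a comparison of operating time is missing. Section 9.2.4.3 records "Duration of the surgical procedure", but sections 4 and 5 do not make it an objective or outcome. The synopsis remark about longer surgery concerns the bone-tendon-bone graft, which neither arm receives.
- A reader might take the local-language summary to make complications a primary outcome. Section 5.1 names tunnel volume alone; the mismatch is editorial.

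**Conclusion.** The point holds as a gap between objective and analysis. Section 11.4.6 does not define the quantity that section 4.4 calls for, namely the proportion of patients per arm with a complication over follow-up, and it attaches no precision to any count. Sections 8.8 and 7.4 leave unclear whether patients with a device complication or rerupture are included. The primary efficacy result is not affected.

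The illustrative upper limit of 12.3% assumes 28 patients in the arm, no events, complete observation and a two-sided 95% limit. It becomes 13.7% with 25 patients, and 10.1% if a one-sided limit is used for 28. The 2% and 5% risks and the 3/28 v 0/28 example are illustrations, not figures from the documents.

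**What to change.** In section 11.4.6, add:

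1. For any intra- or postoperative complication, any serious adverse event and each finding listed in section 10.1.1, the number of randomised patients per arm with at least one event over the whole follow-up. Each patient is counted once for each of these, by onset date.
2. A statement that this safety set includes patients excluded or withdrawn under sections 8.8 and 7.4, with those two sections reconciled to it.
3. An exact two-sided 95% confidence interval for each arm and a risk difference with a 95% confidence interval (for example Newcombe), without a test.
4. The by-visit tables kept as supplementary.

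Operating time may be summarised by arm as an optional descriptive item.

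The cost is a few lines of text and two more tables from data already recorded. The downside is that the intervals will be wide and the safety statement will look less favourable than bare counts would.

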11.4.7 Deviation(s) from the Original Statistical Plan

All deviations from the original statistical analysis plan will be provided in the final clinical study report.

11.5 Handling of Missing Data

Missing data will be left missing, i.e. no imputation scheme will be used. All data from a subject will be used for analysis, irrespective of possibly missing values.

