11.2 Determination of Sample Size

For the power calculation a dedicated software (G*Power [84]) was used. It is aimed to detect a 20% difference in relative change of bone tunnel volume between the two groups. Pooling the standard deviations of the percentage volume change of different bone tunnel sections (articular/outside third) and two different tunnels (anteromedial/posterolateral tunnel) from the study conducted by Araki et al. [85] yields an estimate for the overall standard deviation of $\pm 25.175\%$. With a type I error rate of $\alpha=0.05$ and a power of $1-\beta = 0.8$ and assuming both samples to be normally distributed and having equal variances, the required sample size per group is $n = 25$.

Accounting for a drop-out rate of 10% the total number of subjects for equally sized groups to be acquired is $N = 56$.

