11.4 Planned Analyses

In all statistical analyses testing a significant difference in central tendency between the two groups, significance is set at $\alpha = 0.05$. All statistical tests will be two-sided. The results of these tests will be reported in 95% confidence Interval and p-value for the Student's t-test and in Mann-Whitney U and p-value for the Mann-Whitney U test.

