11.4.1 Datasets to be analyzed, analysis populations

Statistical analysis is based on the intention-to-treat analysis. In the case of the current trial this means that patients not following the rehabilitation protocol will not be excluded from analysis.

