11.4.2 Primary Analysis

Confirmatory analysis is performed on the null hypothesis of equal relative changes in bone tunnel volume from baseline to last CT follow-up (follow-up 3, Visit 5) between the two groups. To make appropriate assumptions on the distribution of the data, the Kolmogorov-Smirnov Test is used to test for significant departure from normality. Significance is set at $\alpha = 0.05$. In case the assumption of normality holds, a Student's t-test is performed to test for a significant difference in means between the two groups. In case the normality assumption is violated, a Mann-Whitney U test is applied. Mean values and standard deviations will be reported. The same procedure will be applied on the dataset of the first CT-follow-up (Visit 4) in the mode of a supportive analysis.

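### The primary 12-month comparison leaves out patients without a 12-month CT and ignores their 4.5-month CT: a small loss of precision, and a bias if loss depends on early widening

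*Combined protocol and SAP*

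**What the plan says.** Section 5.1 sets the primary outcome as the relative change in CT-measured femoral tunnel volume at 12 months. Section 11.4.2 compares it between arms at Visit 5 with a Student's t-test, or a Mann-Whitney U test if a Kolmogorov-Smirnov test rejects normality.

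The 4.5-month CT (Visit 4) is handled apart: "The same procedure will be applied on the dataset of the first CT-follow-up (Visit 4) in the mode of a supportive analysis". The ANCOVA in section 11.4.2.1 also treats the two visits as separate outcomes, and the Visit 4 value is not among its listed covariates.

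On missing values, section 11.5 states "Missing data will be left missing, i.e. no imputation scheme will be used", followed by "All data from a subject will be used for analysis, irrespective of possibly missing values". Section 11.4.1 states "Statistical analysis is based on the intention-to-treat analysis", which it explains only as keeping patients who depart from the rehabilitation protocol. Drop-out is met by enlarging the sample by 10% (sections 11.2 and 11.6). No sensitivity analysis for missing CTs is planned.

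**The concern.** A t-test at Visit 5 needs a Visit 5 value. With nothing imputed and no model linking the two CT visits, a patient lost between 4.5 and 12 months falls out of the 12-month estimate. Section 11.5 promises to use all of a subject's data but names no method that would do this for the primary endpoint.

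Two things are at stake. The first is precision: section 6.1.1 cites a study in which widening occurred mainly at 3 to 6 months, so the 4.5-month scan should say a good deal about the 12-month one. The second is bias: enlarging the sample restores numbers, but it does not correct an estimate from patients who remained for reasons connected with widening.

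**Working it through.** **Inputs.** From section 11.2: difference 20 points, SD 25.175, alpha 0.05, power 0.80, 25 per group, 10% drop-out, N = 56 (28 per arm). From section 11.4: "All statistical tests will be two-sided". Assumed, because the documents do not give them: the Visit 4-5 correlation ρ (0.5, 0.7, 0.9), the timing of loss, and the loss mechanisms.

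**1. The plan's figure.** n = 2 × (1.960 + 0.842)² × (25.175/20)² = 24.9, so 25 per group. 50/0.9 = 55.6, so 56. Both reproduce. (With the exact noncentral t, power at 25 per group is 78.6%, and 26 would be needed for 80%.)

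**2. Precision under random loss.** With 10% missing at Visit 5, 28 × 0.9 = 25.2 per arm remain and the SE is 25.175 × √(2/25.2) = 7.09. If a share m of patients lacks Visit 5 but all have Visit 4, a two-visit likelihood analysis multiplies the variance by 1 − ρ²m.

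| ρ | variance factor, m = 0.10 | SE | power | power at m = 0.20 |
|---|---|---|---|---|
| completers only | 1 | 7.09 | 79% | 74% |
| 0.5 | 0.975 | 7.00 | 80% | 76% |
| 0.7 | 0.951 | 6.92 | 81% | 78% |
| 0.9 | 0.919 | 6.80 | 82% | 81% |

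The gain is about 1 to 3 power points at the planned loss. If only half of those lost had a Visit 4 CT, power would be 79.4 / 80.0 / 80.6% against 78.9%. If loss by 12 months were 5%, all with a Visit 4 CT, it would be 81.6 / 82.1 / 82.7% against 81.1%.

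**3. Loss related to early widening, same mechanism in both arms.** The log-odds of loss rise by 1 per SD of Visit 4 widening, with 10% lost overall and a true difference of −20 at both visits. The completers' difference is −19.4 / −19.1 / −18.8 for ρ = 0.5 / 0.7 / 0.9. It shrinks because controls, who widen more under the alternative, lose more patients (13.2% against 6.9%). With no treatment effect the bias is about zero. At 28 per arm and ρ = 0.7, type I error is 5.1% and power 76%. At 20% loss the estimates are −18.9 / −18.5 / −18.0.

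**4. Loss related to early widening in one arm only.** Suppose 40% of controls in the top fifth of Visit 4 widening are lost, and 5% of everyone else. Control loss is 0.2 × 0.40 + 0.8 × 0.05 = 12%, against 5% in the intervention arm (8.5% overall). In SD units the top fifth has mean 1.40 and the rest −0.35, so the retained controls have mean (0.2 × 0.60 × 1.40 − 0.8 × 0.95 × 0.35)/0.88 = −0.111 at Visit 4. At Visit 5 this lowers the control mean by ρ × 25.175 × 0.111 = 1.4 / 2.0 / 2.5 points. Simulation with 28 per arm gives 1.4 to 2.6 points and t-test power 0.70 to 0.74; the two-visit estimate is unbiased, with power 0.80 to 0.82. The shift does not depend on the true effect, so it is also present under the null. The same mechanism confined to the intervention arm would reverse its sign.

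**The case against.** The strongest reply is that nothing in the documents says widening drives loss, least of all in one arm. Section 6.3.2 blinds patients and withholds their images, so they cannot leave because of what a CT shows. Section 3.1.1 says widening may not affect laxity or failure rates, which weakens the path from widening to symptoms and drop-out. This stands as an argument about likelihood. It does not make the mechanism impossible: section 3.4 links poor graft integration to both graft failure and widening, and section 7.4 removes patients with re-rupture.

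The precision point is also small. The 10% enlargement already covers the lost numbers, and the 1 to 3 points are a best case, since section 11.2 attaches no time to the drop-out rate and the synopsis ties its calculation to a 2-year follow-up. This stands in full.

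Some stronger readings are tempting, and the documents do not support them:

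- That the t-test is valid only if loss is unrelated to widening. Step 3 shows that a mechanism common to both arms leaves the null comparison unbiased.
- That patients without a 12-month CT are discarded from the trial. Those with a 4.5-month CT still enter the Visit 4 supportive test and the Visit 4 ANCOVA; they are missing only from the 12-month estimate.
- That false-positive risk is seriously inflated. If the widest controls, and only they, are lost (20% of that arm, 10% overall), type I error reaches 13.7% and power falls to 51% at ρ = 0.7. That is an extreme assumption with no support in the text.
- That a joint model would restore intention-to-treat. It would not undo the exclusions for re-rupture (section 7.4) or for intra-operative complications with the device (section 8.8).

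**Conclusion.** The point holds in a limited form. The confirmatory analysis omits every randomised patient without a 12-month CT and ignores that patient's 4.5-month scan, and no planned analysis examines what this does to the result. At 10% loss the cost is at most about 1 to 3 power points. Under widening-related loss common to both arms, the estimate is pulled about 1 point toward zero (0.6 to 1.2) if the device works, and is unbiased if it does not. Material bias in both situations needs the loss mechanism to differ between arms, which is possible but not stated anywhere.

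These sizes rest on an assumed correlation of 0.5 to 0.9, normal outcomes with the plan's SD, and, for the upper end of the precision gain, a Visit 4 CT for every patient lost. The change is worth making because it is cheap and uses scans already scheduled, not because the planned test is unsound.

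**What to change.** In sections 11.4.2 and 11.5, make the primary analysis a mixed model for repeated measures on relative volume change at Visits 4 and 5. Include arm, visit and arm-by-visit, an unstructured covariance, and Kenward-Roger or Satterthwaite degrees of freedom, which matter with about 25 per arm. Include every randomised patient with at least one follow-up CT. The primary result is the arm contrast at Visit 5.

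Keep the Visit 5 t-test, or the Mann-Whitney U test if the data are clearly non-normal, as a sensitivity analysis. State that the normality test no longer chooses the primary method.

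The cost is an amendment to the wording and a little more analysis work; no scans, visits or patients are added. The text should be fixed before the interim look at the 4.5-month data.

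The downside should be written into the plan. The model relies on loss being random given the Visit 4 value. It does not help with loss before Visit 4 or with loss driven by unseen 12-month widening, and a patient with no follow-up CT is still left out. The re-rupture and intra-operative exclusions have to be reconciled with the intention-to-treat statement separately.
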